#### **6.4 Weekly Visits (approximately 50 minutes)**

At each weekly visit, subjects in both medication groups will receive medical management (MM) [33]. This provides a basic clinical intervention that was designed to be used in conjunction with prescribed medication, and to be easily implemented by medically trained practitioners in non-specialty settings. The treatment will support subjects' efforts to reduce their drinking.

The first session (conducted right after the first MRI scan) will consist of a review of the results of the initial evaluation, identifying any medical concerns. This session will also use the brochure *A Guide to Sensible Drinking*, developed for use in the World Health Organization Brief Intervention Study project. The subject is then provided with a rationale and information about pharmacotherapy and the importance of adherence. At each visit, assessment and counseling (lasting approximately 15 minutes) are conducted. During these sessions, the nurse will perform a medical check on the subject's general functioning, obtain vital signs and weight, ask about medication side effects and concurrent medications, monitor the subject's medication adherence, and as appropriate, make recommendations on strategies for medication adherence for the subject to follow until the next visit. Men will be advised to consume no more than 4 standard drinks per day and 12 standard drinks per week and women will be advised to consume no more than 3 drinks per day and 8 drinks per week. Because subjects will not be physically dependent on alcohol, reduction of heavy drinking is a safe and ethical goal. The research technician or coordinator will measure the subject's breath alcohol concentration, perform a brief assessment of the subject's drinking, review the self-administered BDI to assess suicidal thoughts/ideation (and discuss with the nurse and/or physician, if there is endorsement of suicidal thoughts). For patient safety during travel, subjects will be instructed not to drink prior to study visits. At each visit, the subject's BrAC, weight, and vital signs will be measured. Subjects must have a breath alcohol level of 0.00 g% to complete the screening visit, 2 lab MRI scan visits, and endpoint visit, and below 0.05 g% to complete the weekly study visits. Study staff will follow TRC standard operating procedures for all subjects that present with a breath alcohol level above 0.00 g% at study visits.

Throughout the study, if a subject misses a study visit due to a vacation or an unforeseen event, the study nurse will provide the subject with enough study medication to ensure that he or she will be able to maintain the daily dosage of study medication until the next scheduled visit. The nurse will also provide instructions on how to take the study medication as per the dosing schedule. Study nurses will instruct subjects to call the TRC at any time to discuss any problems or concerns they may have while taking the study medication. All subjects will be provided phone numbers to contact the study staff during office hours and the beeper number for off-hours contact 24 hours a day. Subjects will be asked to come in for their next study visit as soon as possible.

If a subject calls to cancel a scheduled study visit due to an unforeseen event, study personnel will reschedule the study visit for as soon thereafter as possible. Study staff will mail the study medication to the subject via registered mail under the supervision of a study nurse. Staff will mail the study medication with the intent to reach the subject, before he or she runs out of study medication. The subjects will only be provided with enough study medication to ensure that they will be able to maintain their daily dosage of study medication until their next scheduled visit. The nurse will provide instructions over the phone on how to take the study medication as per the dosing schedule and record any adverse events that have occurred since the last study visit. Study nurses will instruct subjects to call the TRC at any time to

CONFIDENTIAL

This material is the property of the University of Pennsylvania. Do not disclose or use except as authorized in writing by the study sponsor

discuss any problems or concerns they may have while taking the study medication. Study staff will make efforts to reschedule missed study visits as soon as possible. An investigator will determine how many additional weeks of study medication a subject will be allowed to receive without attending a study visit.

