### **Schedule of Assessments**

Instrument	Visit 0 Screening	Visit 1 MRI	Visits 2-6	Visit 7 MRI	Visit 8	Visit 9 Endpoint
Breath Alcohol Concentration & Vital signs	X	X	X	X	X	X
Study Overview & Informed Consent	X					
Medical History & Physical Exam	X					
Laboratory tests (Blood for CBC, GGTP, HIV and DNA)						X (GGTP only)
MRI video	X					
MRI safety sheet (metal)	X	X		X		
Urine pregnancy test	Females	Females		Females		
Urine drug toxic screen	X	X		X		
Blood sample (2 Tbsp)	Females	Females		Females		
Demographic interview	X					
Structured Clinical Interview for DSM	X					Alcohol Module Only
Wechsler Abbreviated Scale of Intelligence	X					
Timeline Follow-Back Interview	X	X(brief)	X(brief)	X(brief)	X(brief)	X(brief)
Beck Depression Inventory	X	X	X	X	X	X
Short Index of Problems	X			X		X

CONFIDENTIAL

This material is the property of the University of Pennsylvania. Do not disclose or use except as authorized in writing by the study sponsor

Fagerstrom Test of Nicotine Dependence	X					X
Obsessive Compulsive Drinking Scale	X	X		X		X
Alcohol Urge Questionnaire	X	X		X		X
Within Session Rating Scale		X		X		
Clinical Institute Withdrawal Assessment for Alcohol Scale	X	X		X		
CogBias Tasks		X		X		
Cogstate Battery		X		X		X
Controlled Oral Word Association test		X		X		
Digit Span		X		X		
Medical Management		X	X	X	X	X
Endpoint/Termination Form						X
Medication Questionnaire						X
Measures of Treatment		X	X	X	X	X

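### Section 6.4 allows study drug in unattended weeks but states no remote equivalent of the BDI review for suicidal thoughts

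*Combined protocol and SAP*

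**What the plan says.** Section 6.4 describes the attended weekly visit and then two ways of continuing drug without one.

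- **Attended visit.** Research staff "review the self-administered BDI to assess suicidal thoughts/ideation". When the form raises a concern, their instruction is to "discuss with the nurse and/or physician, if there is endorsement of suicidal thoughts". The Schedule of Assessments marks the "Beck Depression Inventory" at every visit, 0 to 9.
- **Missed visit** (vacation or unforeseen event, throughout the study). The nurse gives enough drug to "maintain the daily dosage of study medication until the next scheduled visit". Subjects are told that they may call at any time, and they have an off-hours beeper number. On dosing, the paragraph states: "The nurse will also provide instructions on how to take the study medication as per the dosing schedule".
- **Cancelled visit.** Drug is mailed, and the amount is limited to what lets subjects "maintain their daily dosage of study medication until their next scheduled visit". The remote contact is set out as follows: "The nurse will provide instructions over the phone on how to take the study medication as per the dosing schedule and record any adverse events". The adverse events meant are those arising after the preceding visit.
- **Limit.** "An investigator will determine how many additional weeks of study medication a subject will be allowed to receive without attending a study visit".

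Both paragraphs also ask for the visit to be rescheduled as soon as possible. Titration weeks are not excepted. Neither paragraph mentions the BDI or a question about suicidal thoughts.

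**The concern.** Section 4.4.1 withdraws subjects with severe psychological symptoms and gives suicidal thoughts as its example. Section 1.4 lists depression and mood problems in 5–9% of patients on topiramate. The BDI review is the protocol's scheduled means of finding suicidal thoughts, and a withdrawal rule works only if its trigger is detected. A site that follows 6.4 exactly can keep a subject on drug, possibly during dose escalation, past the date on which that screen was due, with nothing in its place.

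The investigator's discretion over the number of unattended weeks is not the fault. It is a reasonable clinical control. What is missing is the screen during those weeks.

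**Working it through.** The plan gives no figure of its own to reproduce. The check is a count from its schedules.

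**Inputs**
- Visits are weekly, 7 days apart (Table 1; 6.4).
- BDI on drug: Visits 2–6, 7 and 8, so 5 + 1 + 1 = 7 reviews. Visit 1 precedes the first dose and Visit 9 follows the taper.
- Daily dose in weeks 1–7: 25, 50, 75, 100, 150, 200 and 200 mg (Table 1). The dose rises at Visits 2–6, which is 5 steps.
- Each dispensing holds 8 days of drug (5.7).

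**Interval between BDI reviews when one visit slips by s days**
- Interval = 7 + s days.
- The 8-day supply covers s = 1. Extra supply under 6.4 is needed when 7 + s > 8, that is, s ≥ 2.
- Made up before the next visit (s = 2 to 6): 7 + 2 = 9 to 7 + 6 = 13 days.
- Not made up: 7 + 7 = 14 days.
- With full attendance: 7 days.

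**Does a dose step fall in the interval?** The text supports two readings. Both paragraphs say that the supply is to maintain the daily dosage, which suggests holding the dose. Both also refer to the dosing schedule, which suggests that the dose keeps rising. Take Visit 6 missed and not made up. The last BDI is at Visit 5 (after week 4, 100 mg/day) and the next at Visit 7 (after week 6).

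| Reading | Days between reviews | Dose before first and second review | Steps in interval | Steps with no BDI at that step |
|---|---|---|---|---|
| Follow schedule | 14 | 100 and 200 mg/day | 2 (100→150, 150→200) | 1 |
| Hold dose | 14 | 100 and 150 mg/day | 1 (100→150) | 0 |
| All visits attended | 7 | one step apart | 1 | 0 |

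The longer interval arises on either reading. The unscreened dose step arises only on the first.

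**What else applies in an unattended week?**
- 8.2: adverse events are sought by specific questioning at each contact.
- 8.6: subjects are evaluated weekly on drug, and a physician is available at all times.
- 10.1: the principal investigator reviews adverse events at least weekly.
- 6.4: 24-hour contact numbers.

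All remain in force. None names suicidal thoughts or the BDI, and none gives a remote procedure for them.

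**The case against.** The best reply is that detection of mood change does not stop. Any symptom that develops or worsens is an adverse event (8.1), the nurse must ask at each contact, and the mail route already requires a telephone adverse-event check. Section 8.6 states a weekly evaluation duty that 6.4 does not waive. Entry criteria exclude a history of suicidal intent and current major Axis I disorders other than alcohol, nicotine and cannabis use disorders. Missed visits are rescheduled promptly, so the BDI is usually deferred and not lost. The study manual described in 10.1 may hold a telephone procedure, but it is not among the documents.

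Much of this stands, and it confines the point to one named screen. It does not close the gap. At attended visits the protocol has the nurse ask about side effects and also has staff review the BDI, so it does not treat the first as a substitute for the second. Contact numbers depend on the subject calling. Exclusion at entry does not detect symptoms that emerge on drug. Section 6.4 is the text that permits the supply, and it is silent on the screen.

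A reader might infer something stronger: that a subject could miss Visits 2–6 and be raised from 25 to 200 mg/day over six weeks without safety contact. No text caps the number of weeks, but the documents do not support that picture. An investigator must agree to each extension, visits are to be rescheduled, adverse-event questioning and weekly evaluation continue, non-adherence can lead to withdrawal (4.4.1), and the dose may not rise at all on the hold reading.

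**Conclusion.** The point holds in limited form. Following 6.4 as written can continue study drug without the protocol's own scheduled screen for a withdrawal trigger. For one missed visit that needs extra supply, the interval between BDI reviews is 9–14 days in place of 7. On the schedule-following reading, one dose step can occur with no BDI at that step; on the hold reading, none does. The day counts assume visits exactly 7 days apart and that all of the 8-day supply is used.

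A reader might multiply the 5–9% rate by the 20 topiramate subjects and treat the result as cases at risk of being missed. That is not supported. The rate covers depression and mood problems, not suicidal ideation, and the documents give no missed-visit rate, so no expected count is claimed. The severity is modest, and the case for acting rests largely on how little the remedy costs.

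**What to change.** In both the missed-visit and cancelled-visit paragraphs of 6.4:

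- Require a nurse telephone contact in each week in which a scheduled visit is not attended, at or near the missed visit date, however and whenever the drug was supplied. Tying the check to the supply contact alone would add nothing when drug is handed over before a vacation or for several weeks at once.
- At that contact, give the BDI suicidal-ideation item (or the full BDI) with the adverse-event questions, and use the existing escalation to nurse or physician. Mark on the CRF that it was done by telephone, since the BDI is otherwise self-administered.
- Do not raise the dose until this is done. If the subject cannot be reached, continue the current dose and have the study physician decide on further supply or taper. Withholding all drug could stop treatment abruptly, without the planned six-day taper (Table 1).
- Leave the number of unattended weeks to the investigator.

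A call at the missed visit date splits a 14-day interval into two of about 7 days, and the rule works on either reading of the dosing text. The cost is a call of a few minutes per unattended week and an occasional delayed dose step. It applies identically in both arms, so the blind is unaffected.

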## **6.5 Laboratory/MRI Session 2 Visit (approximately 3.5 hours)**

During week 7, subjects will complete the 2nd scanning session. Procedures for the Laboratory/MRI Session 2 visit are the same as the 1st Laboratory/MRI Session procedures.

Early Termination Visit:

All patients (including those who discontinue treatment prematurely) will be asked to complete an end-of-treatment evaluation and to complete all scheduled assessments to facilitate intention-to-treat (ITT) analyses. All patients will be informed of these procedures prior to study enrollment. Patients will be compensated \$50 for completing the end-of-treatment visit. Patients who decide to terminate the study prior to week 8 will also receive \$50 upon completion of the end-of-treatment procedures. For patients who withdraw early and do not wish to continue with study visits/procedures, all end-of-treatment procedures will be administered at the time of withdrawal. Such patients will also be asked to undergo in-person or telephone follow-up at end-of-treatment for collection of the remaining treatment-phase Timeline Follow-back data.

## **6.6 Endpoint Visit (approximately 2 hours)**

Following study drug taper, subjects will complete the Endpoint visit. During this visit, subjects will complete: 1) a breathalyzer to ensure a BrAC of 0.00 g%, 2) a blood draw (GGTP only), 3) brief questionnaires (including BDI for suicidal ideation,, and Endpoint visit), 4) Cogstate battery, and 5) Medication Questionnaire. Subjects will be eligible to request and receive de-briefing after completing the Endpoint Visit. The procedure for debriefing subjects involves the following: (1) study staff informs subjects at the Endpoint Visit that they are eligible to learn from the pharmacy whether they received active medication or placebo during the study, (2) if the subject wishes to receive this information, study staff will provide UPENN IDS an envelope with postage and the subject's address, along with the "Pharmacy Debriefing" sheet, which notes the subject's name & ID#, (3) the pharmacy technician will mail the subject the appropriate letter indicating the medication assignment, (4) study staff will remain blinded to study medication assignment.

### **Schedule of Assessments**

Instrument	Visit 0 Screening	Visit 1 MRI	Visits 2-6	Visit 7 MRI	Visit 8	Visit 9 Endpoint
Breath Alcohol Concentration & Vital signs	X	X	X	X	X	X
Study Overview & Informed Consent	X					
Medical History & Physical Exam	X					
Laboratory tests (Blood for CBC, GGTP, HIV and DNA)						X (GGTP only)
MRI video	X					
MRI safety sheet (metal)	X	X		X		
Urine pregnancy test	Females	Females		Females		
Urine drug toxic screen	X	X		X		
Blood sample (2 Tbsp)	Females	Females		Females		
Demographic interview	X					
Structured Clinical Interview for DSM	X					Alcohol Module Only
Wechsler Abbreviated Scale of Intelligence	X					
Timeline Follow-Back Interview	X	X(brief)	X(brief)	X(brief)	X(brief)	X(brief)
Beck Depression Inventory	X	X	X	X	X	X
Short Index of Problems	X			X		X

CONFIDENTIAL

This material is the property of the University of Pennsylvania. Do not disclose or use except as authorized in writing by the study sponsor

Fagerstrom Test of Nicotine Dependence	X					X
Obsessive Compulsive Drinking Scale	X	X		X		X
Alcohol Urge Questionnaire	X	X		X		X
Within Session Rating Scale		X		X		
Clinical Institute Withdrawal Assessment for Alcohol Scale	X	X		X		
CogBias Tasks		X		X		
Cogstate Battery		X		X		X
Controlled Oral Word Association test		X		X		
Digit Span		X		X		
Medical Management		X	X	X	X	X
Endpoint/Termination Form						X
Medication Questionnaire						X
Measures of Treatment		X	X	X	X	X

## 7 Statistical Plan

### 7.1 Sample Size Determination

The current sample size is based on the need to pilot our alcohol and non-alcohol audio-visual videos both on- and off-magnet through computerized tasks and during pCASL perfusion fMRI scanning.

### 7.2 Statistical Methods

#### 7.2.1 Imaging Data Processing

Prior to performing analyses, brain data are examined for gross movement and full image acquisition. A Statistical Parametric Mapping (SPM)-based ASL data processing toolbox is used for data analyses. ASL image pairs are realigned to the mean of all control images and spatially smoothed with a 3D isotropic Gaussian kernel with full width at half maximum of 10mm. CBF image series are generated using a simplified two-compartment model with the sinc interpolation method for CBF calculations. The mean control image of each subject's data is co-registered to a high-resolution 3D T1 structural image using the mutual information based co-registration algorithm provided by SPM8. The same co-registration parameters are used to co-register the CBF maps to the structural image. The structural image is then spatially normalized to the Montreal Neurological Institute (MNI) standard brain. The same parameters are used to normalize the CBF images to the MNI standard space. Each subject's normalized mean control images are segmented using SPM8. The segmented gray matter masks are averaged and the overlap of subject's gray matter is extracted. This final mask is used for calculating global CBF for each session.

#### 7.2.2 Imaging Data Analyses

Global CBF time course will be included in the model as a covariate to examine the effects of topiramate on regional CBF. No temporal smoothing will be applied. Contrasts between conditions (alcohol cue vs non-alcohol cue; scan 1 vs scan 2) will be defined in the general linear model to assess the voxel by voxel CBF difference. Using the corresponding parametric maps of this contrast ( $\beta$  maps), random effects analysis will be employed to test for a significant main effect of condition with a statistical parametric map of the T statistic at each voxel for population inference for each session for the placebo and topiramate groups (second-level analysis). A 2x2 factorial design matrix will be used to assess the effects of the pharmacological manipulation by including the group (topiramate vs placebo) and condition (scan 1 vs scan 2) as the two factors. An associated contrast will be defined in this model to examine administration effects. This two-stage analysis is theoretically equivalent to a 2-way analysis of variance (ANOVA). Simple regression analyses will be conducted on CBF with the change in craving scores [post-alcohol cue minus pre-alcohol cue craving scores, number of heavy drinking days during the past 30 days, and age] as covariates of interest to test for prognostic brain/behavioral correlations. For the exploratory aim, subjects will be grouped by genotype (CC vs A-allele carrier) to examine the moderating effects of rs2832407 in

CONFIDENTIAL

This material is the property of the University of Pennsylvania. Do not disclose or use except as authorized in writing by the study sponsor

*GRK1* on topiramate effects using the same simple regression analyses described above. We will limit this analysis to European Americans, as that is the population in which the preliminary findings were obtained and allele frequencies differ significantly by population.

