## 2 Study Objectives

**Objective 1** Pilot cue sets (see Appendix 1) and confirm brain and behavioral responses to alcohol cues in individuals with AUD using pCASL fMRI

**Hypothesis 1:** Similar to our other pCASL fMRI cue-reactivity studies in drug-dependent individuals, subjects will exhibit greater brain activity in the interconnected VS and medial orbitofrontal cortex (mOFC) during alcohol cue exposure compared to non-alcohol cue exposure.

**Objective 2a** Demonstrate neuromodulatory effects of a GABA/glutamate modulator, topiramate, on RB and alcohol cue reactivity

**Hypothesis 2a:** We hypothesize that topiramate will ameliorate neurophysiological vulnerabilities by dampening neural activity in the brain 'at rest' and during alcohol cue exposure in reward-related regions, such as the amygdala, mOFC, VS, and the insula. In contrast, neural activity in placebo-treated individuals at rest and in alcohol cue reactivity will not differ from pre- to post-treatment.

**Objective 2b** Examine the mechanism underlying topiramate's ability to blunt alcohol cue reactivity and reduce heavy drinking days

**Hypothesis 2b:** We hypothesize that there will be a direct relationship between RB in the VS and mOFC and its effects on alcohol cue reactivity. Although overall effects are expected, reductions in heavy drinking days will correlate with topiramate's ability to modulate reward circuitry responses.

**Exploratory Objective** Examine the moderating effects of rs2832407 on topiramate's effects on brain and behavioral responses

**Exploratory hypothesis:** C-allele homozygotes at this locus will show the most robust effects of topiramate.

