## 3 Study Design

### 3.1 General Design

- **Phase IV Study** - This is a phase IV research study aimed at identifying the brain and behavioral mechanisms underlying the GABA/glutamate modulator, topiramate.
- **Design** – Heavy drinkers who meet DSM-5 criteria for AUD and express an interest in reducing or stopping drinking will be recruited, screened, consented, and if eligible, will complete a randomized double-blind, placebo-controlled study of topiramate ( $N=40$ ; topiramate 200 mg/day:  $n=20$  or placebo:  $n=20$ ). Topiramate or placebo will be initiated after Scan 1 and continued with weekly visits and medical management [33]. During the 7th week, participants will complete Scan 2 followed by medication taper and an endpoint visit. We will use perfusion fMRI during alcohol cue exposure to acquire brain and behavioral responses to alcohol cues. The goals of this study are to pilot test the validity of our alcohol cues and to identify brain and behavioral mechanisms of topiramate in reducing heavy drinking in alcohol dependent individuals.
- **Study Duration** – The duration of this study will be approximately 9 weeks, including screening, Scan 1, 8 weeks of medication and medical management (including medication taper), Scan 2 during week 7, medication taper, and an endpoint visit. The entire study will run for approximately 24 months.

CONFIDENTIAL

This material is the property of the University of Pennsylvania. Do not disclose or use except as authorized in writing by the study sponsor

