### 5.3 Method for Assigning Subjects to Treatment Groups

Subjects will be randomly assigned to one of two treatment conditions: topiramate 200 mg/day (n = 20) or placebo (n = 20). Study staff and the Investigational Drug Service (IDS) staff will be responsible for medication randomization. The process for randomization is: 1) Research coordinator will complete an "randomization form," which includes the variables to be entered into the block randomization program by study staff (i.e., sex, number of heavy drinking days in the past month( >12 heavy drinking days and =<12 heavy drinking days)); 2) study staff will enter variables into the block randomization program, 3) study staff will fax randomization group to IDS, who will assign a kit number to subject and fax kit assignment to research coordinator; 4) the research nurse or Physician will dispense medication to subject and complete and sign IDS Rx prescription form included in starter kit. 5) Research coordinator will fax completed form to IDS. The medication will be dispensed using the above dosing schedule. To maintain double-blind conditions, study staff responsible for randomization will not be involved in subject participation, study visits, or data collection.

Study drug for subsequent visits will be ordered by the research coordinator using the "Research Pharmacy Schedule" form, a copy of which will be retained in the subject's research file. At each visit, a supply of

CONFIDENTIAL

This material is the property of the University of Pennsylvania. Do not disclose or use except as authorized in writing by the study sponsor

study drug will be dispensed by the research nurse. Subjects with severe psychological symptoms or determined to be inappropriate for the study by an investigator will be withdrawn from the study. Subjects who are withdrawn completely will be referred for appropriate clinical care.

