### **7.2.3 Behavioral Analyses**

Statistical significance tests use an alpha of .05 unless otherwise noted. Continuous demographic variables (e.g., age, education, quantity/frequency of alcohol use) are checked for normality, transformed if necessary, and summarized by calculating means, standard deviations and ranges. Scores on each factor will be included as covariates of interest with respect to perfusion fMRI data and genetic variance. Analysis of variance will be used to assess demographic differences across groups. Nominal demographic variables (e.g., race, sex, genotype) are summarized by calculating proportions and compared across groups using chi square analyses. Demographic (age, years education, monthly income) and clinical (depression, anxiety) will also be summarized.

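### The group-by-scan drug test in Section 7.2.2 is valid if paired, but does not adjust for Scan 1 CBF, a pre-dose baseline already in hand

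*Combined protocol and SAP*

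**What the plan says.** Section 7.2.2 (Imaging Data Analyses) assesses the drug effect in a 2x2 factorial matrix "including the group (topiramate vs placebo) and condition (scan 1 vs scan 2) as the two factors". The only adjustment covariate stated for regional CBF is the global CBF time course. On the test itself the section adds only this: "An associated contrast will be defined in this model to examine administration effects". It likens the two-stage procedure to a two-way ANOVA.

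Three other places bear on the point:

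- Section 3.1 (General Design) fixes the timing of the first scan: "Topiramate or placebo will be initiated after Scan 1".
- Section 5.3 (treatment assignment) feeds two variables into the block randomisation, "sex, number of heavy drinking days in the past month", the second cut at 12 days. Neither is a term in the 2x2 model. Section 7.2.2 does mention "number of heavy drinking days during the past 30 days", but as a covariate of interest in separate brain/behaviour regressions.
- Section 7.2.3 (Behavioral Analyses) says "Scores on each factor will be included as covariates of interest with respect to perfusion fMRI data". It does not define the factors, and it names neither Scan 1 CBF, sex nor the drinking stratum.

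Hypothesis 2a in Section 2 predicts a fall in activity on topiramate, while "neural activity in placebo-treated individuals at rest and in alcohol cue reactivity will not differ from pre- to post-treatment".

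**The concern.** The 2x2 model carries Objective 2a. In it Scan 1 is a level of the scan factor, so the group-by-scan contrast removes each subject's Scan 1 value by subtraction, with its coefficient fixed at one. When the correlation between scans is below one, that over-corrects and carries Scan 1 noise into the estimate. Fitting Scan 1 as a covariate lets the data set the coefficient. Because Scan 1 precedes the first dose, treatment cannot have affected it, and adjustment is safe.

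What is at stake is precision. The trial plans 20 subjects per arm, and Section 7.1 gives no effect size, variance or power, so nothing in the plan shows that precision is already sufficient. The covariate is already being collected.

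**Working it through.** The plan states no power or detectable effect, so there is no figure of its own to reproduce.

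**Inputs from the documents.** n = 20 per arm (Sections 3.1 and 5.3). Alpha 0.05 (Section 7.2.3), taken as two-sided because sidedness is not stated.

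**Assumptions.** One scalar outcome, such as mean CBF in a region. SD of 1 at each scan. Scan-to-scan correlation rho from 0.3 to 0.9. Effect of 0.8 SD at Scan 2. Sex and stratum balanced between arms and given no effect on the outcome.

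**Formulas.**

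- Paired group-by-scan (change score): SE = sqrt(4(1 − rho)/n), 38 df.
- Scan 2 adjusted for Scan 1, sex and stratum: SE = sqrt(2(1 − rho²)/n) × sqrt(1 + 1/34), 35 df. The last factor is the cost of estimating the Scan 1 coefficient.
- Matching n: the smallest n per arm at which the paired test has the power of the adjusted test at 20 per arm (noncentral t).

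**Worked case, rho = 0.5.** Paired: sqrt(4 × 0.5/20) = 0.316. Adjusted: sqrt(2 × 0.75/20) × 1.0146 = 0.2739 × 1.0146 = 0.278. The cut is 1 − 0.278/0.316 = 12%. The variance ratio is 0.1000/0.0772 = 1.295, and 20 × 1.295 = 25.9, so about 26 per arm.

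| rho | SE paired | SE adjusted | SE cut | Power paired | Power adjusted | Matching n per arm |
|---|---|---|---|---|---|---|
| 0.3 | 0.374 | 0.306 | 18.2% | 55% | 72% | 30 |
| 0.5 | 0.316 | 0.278 | 12.1% | 69% | 80% | 26 |
| 0.7 | 0.245 | 0.229 | 6.5% | 89% | 92% | 23 |
| 0.8 | 0.200 | 0.193 | 3.7% | 97.4% | 98.1% | 22 |
| 0.9 | 0.141 | 0.140 | 1.1% | >99.9% | >99.9% | 21 |

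At rho = 0.9 the extra subject is a rounding up: 20 × 1.023 = 20.5. The effect detectable with 80% power falls from 1.08 to 0.88 SD at rho 0.3, from 0.91 to 0.80 at 0.5, and from 0.70 to 0.66 at 0.7.

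**Simulation check** (200,000 trials per rho, at 0.3/0.5/0.7). The SD of the estimates was 0.375/0.317/0.245 paired and 0.306/0.278/0.229 adjusted. Power was 54.7/69.5/88.9% and 72.0/80.0/92.4%. A separate run of 100,000 trials gave a null rejection rate of 5.1/5.0/5.0% for the adjusted test.

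**Randomisation factors.** Adding them to the change-score test gave power 54.8/69.3/88.9%, against 55.0/69.4/88.9% without them in the same run, a difference of at most 0.2 points. The documents do not say how strongly either factor predicts CBF, so no gain is counted for them.

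**The case against.** The strongest reply is that this is a choice between two valid methods in a pilot mechanistic study that claims no power. That is right as to validity: nothing here is an error in the test.

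The size of the gain also depends on rho, which the documents do not give. At 0.8 or above it is small. The calculation further takes all 20 per arm as analysed, while Section 7.3 restricts analysis to protocol-compliant subjects, and it leaves out the global CBF covariate. These points limit the claim to the range shown.

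Feasibility is a fair objection too. The planned analysis is voxel-wise, and the documents do not show that the SPM8-based pipeline in Section 7.2.1 can take a different Scan 1 value at each voxel. Fitting the model on regional means avoids the difficulty. A comparison of change maps is always possible, but gives no Scan 1 gain.

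The 2x2 also speaks directly to the placebo pre/post statement in Hypothesis 2a, which the treatment term of a Scan 2 model does not. That stands, and the within-arm contrasts should stay.

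Three stronger readings are tempting, and the documents support none of them:

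- *The two scans are entered as independent observations.* A nominal 5% group-by-scan test would then have size of about 2.0/0.65/0.06% at rho 0.3/0.5/0.7. But Section 7.2.2 defines a scan 1 versus scan 2 contrast and carries contrast maps to a second level, which is compatible with pairing.
- *The drug contrast might be the group main effect.* Entered unpaired, that would have size of about 8.6/11/13%. Hypothesis 2a, with change on topiramate and none on placebo, implies group-by-scan.
- *Leaving out the randomisation factors invalidates the test or costs known power.* Omitting balanced factors can only make the test conservative, and their prognostic strength is not given.

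**Conclusion.** The point holds as one of precision. The paired group-by-scan test is sound, but it leaves unused a pre-dose baseline that the trial already collects. For a single scalar outcome with 20 analysed per arm, the loss in standard error runs from about 18% at rho 0.3 to about 1% at rho 0.9, or roughly 10 down to 1 subjects per arm. It is material at moderate correlations and negligible at high ones. Rho and the 0.8 SD effect are assumptions, rho may differ between resting CBF and the cue contrast, and the voxel-wise gain is conditional on software. The randomisation factors belong in the model because they were used to allocate treatment, not because a gain has been shown. Pairing and contrast need one clarifying sentence and no more. The change is worth making before unblinding, since a contrast or covariate set chosen after seeing the maps would depend on the data.

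**What to change.** For resting CBF, and for alcohol minus non-alcohol CBF, make the drug test the treatment term in a subject-level model of the Scan 2 value on treatment, Scan 1 value, sex and heavy-drinking-day stratum.

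- Fit it on mean CBF in the regions Hypothesis 2a already names: amygdala, medial orbitofrontal cortex, ventral striatum and insula.
- Fit it voxel-wise as well where the software accepts a voxel-wise covariate. Where it does not, compare Scan 2 minus Scan 1 maps between arms with sex and stratum as covariates. This keeps the pairing without the Scan 1 gain.
- Keep the within-arm scan contrasts for the placebo statement in Hypothesis 2a.
- If the 2x2 is kept, state that scan is a within-subject factor and that group-by-scan is the drug contrast.

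The cost is SAP wording, a revised second-level design matrix and about three degrees of freedom (38 to 35), or two (38 to 36) for the change-map route. No new data are needed.
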